13. STUDY OVERSIGHT AND DATA REPORTING / REGULATORY REQUIREMENTS

Adverse event lists, guidelines, and instructions for AE reporting can be found in Section 10.0 (Adverse Events: List and Reporting Requirements).

13.1 Study Oversight

This protocol is monitored at several levels, as described in this section. The Protocol Principal Investigator is responsible for monitoring the conduct and progress of the clinical trial, including the ongoing review of accrual, patient-specific clinical and laboratory data, and routine and serious adverse events; reporting of expedited adverse events; and accumulation of reported adverse events from other trials testing the same drug(s). The Protocol Principal Investigator and statistician have access to the data at all times through the CTMS web-based reporting portal.

During the Phase 2 portion of the study, the Protocol Principal Investigator will have, at a minimum, quarterly conference calls with the Study Investigators and the CTEP Medical Officer(s) to review accrual, progress, and pharmacovigilance. Decisions to proceed to the second stage of a Phase 2 trial will require sign-off by the Protocol Principal Investigator and the Protocol Statistician.

All Study Investigators at participating sites who register/enroll patients on a given protocol are responsible for timely submission of data via Medidata Rave and timely reporting of adverse events for that particular study. This includes timely review of data collected on the electronic CRFs submitted via Medidata Rave.

All studies are also reviewed in accordance with the enrolling institution's data safety monitoring plan.

13.2 Data Reporting

Data collection for this study will be done exclusively through Medidata Rave. Access to the trial in Rave is granted through the iMedidata application to all persons with the appropriate roles assigned in the Regulatory Support System (RSS). To access Rave via iMedidata, the site user must have an active CTEP IAM account (check at <https://ctepcore.nci.nih.gov/iam>) and the appropriate Rave role (Rave CRA, Rave Read-Only, Rave CRA (Lab Admin), Rave SLA, or Rave Investigator) on either the LPO or participating organization roster at the enrolling site. To hold the Rave CRA role or Rave CRA (Lab Admin) role, the user must hold a minimum of an AP registration type. To hold the Rave Investigator role, the individual must be registered as an NPIVR or IVR. Associates can hold read-only roles in Rave.

Upon initial site registration approval for the study in RSS, all persons with Rave roles assigned on the appropriate roster will be sent a study invitation e-mail from iMedidata. To accept the invitation, site users must log into the Select Login (<https://login.imedidata.com/selectlogin>) using their CTEP-IAM user name and password, and click on the "accept" link in the upper right-corner of the iMedidata page. Please note, site users will not be able to access the study in Rave until all required Medidata and study specific trainings are completed. Trainings will be in the form of electronic learnings (eLearnings), and can be accessed by clicking on the link in the upper right pane of the iMedidata screen.

Users that have not previously activated their iMedidata/Rave account at the time of initial site registration approval for the study in RSS will also receive a separate invitation from iMedidata

to activate their account. Account activation instructions are located on the CTSU website, Rave tab under the Rave resource materials (Medidata Account Activation and Study Invitation Acceptance). Additional information on iMedidata/Rave is available on the CTSU members' website under the Rave tab or by contacting the CTSU Help Desk at [name] or by e-mail at [contact].

13.2.1 Method

For studies assigned for CTMS Routine Monitoring:

This study will be monitored by the Clinical Trials Monitoring Service (CTMS). Data will be submitted to CTMS at least once every two weeks via Medidata Rave (or other modality if approved by CTEP). Information on CTMS reporting is available at: <http://www.theradex.com/clinicalTechnologies/?National-Cancer-Institute-NCI-11>. On-site audits will be conducted on an 18-36 month basis as part of routine cancer center site visits. More frequent audits may be conducted if warranted by accrual or due to concerns regarding data quality or timely submission. For CTMS monitored studies, after users have activated their accounts, please contact the Theradex Help Desk at [contact] or by email at [contact] for additional support with Rave and completion of CRFs.

13.2.2 Responsibility for Data Submission

For ETCTN trials, it is the responsibility of the PI(s) at the site to ensure that all investigators at the ETCTN Sites understand the procedures for data submission for each ETCTN protocol and that protocol specified data are submitted accurately and in a timely manner to the CTMS via the electronic data capture system, Medidata Rave.

Data are to be submitted via Medidata Rave to CTMS on a real-time basis, but no less than once every 2 weeks. The timeliness of data submissions and timeliness in resolving data queries will be tracked by CTMS. Metrics for timeliness will be followed and assessed on a quarterly basis. For the purpose of Institutional Performance Monitoring, data will be considered delinquent if it is greater than 4 weeks past due.

Data from Medidata Rave and CTEP-AERS is reviewed by the CTMS on an ongoing basis as data is received. Queries will be issued by CTMS directly within Rave. The queries will appear on the Task Summary Tab within Rave for the CRA at the ETCTN to resolve. Monthly web-based reports are posted for review by the Drug Monitors in the IDB, CTEP. Onsite audits will be conducted by the CTMS to ensure compliance with regulatory requirements, GCP, and NCI policies and procedures with the overarching goal of ensuring the integrity of data generated from NCI-sponsored clinical trials, as described in the ETCTN Program Guidelines, which may be found on the CTEP (http://ctep.cancer.gov/protocolDevelopment/electronic_applications/adverse_events.htm) and CTSU websites.

An End of Study CRF is to be completed by the PI, and is to include a summary of study endpoints not otherwise captured in the database, such as (for phase 1 trials) the

recommended phase 2 dose (RP2D) and a description of any dose-limiting toxicities (DLTs). CTMS will utilize a core set of eCRFs that are Cancer Data Standards Registry and Repository (caDSR) compliant (<http://cbiit.nci.nih.gov/ncip/biomedical-informatics-resources/interoperability-and-semantics/metadata-and-models>). Customized eCRFs will be included when appropriate to meet unique study requirements. The PI is encouraged to review the eCRFs, working closely with CTMS to ensure prospectively that all required items are appropriately captured in the eCRFs prior to study activation. CTMS will prepare the eCRFs with built-in edit checks to the extent possible to promote data integrity.

CDUS data submissions for ETCTN trials activated after March 1, 2014, will be carried out by the CTMS contractor, Theradex. CDUS submissions are performed by Theradex on a monthly basis. The trial's lead institution is responsible for timely submission to CTMS via Rave, as above.

Further information on data submission procedures can be found in the ETCTN Program Guidelines (http://ctep.cancer.gov/protocolDevelopment/electronic_applications/adverse_events.htm).

13.3 CTEP Multicenter Guidelines

N/A

13.4 Collaborative Agreements Language

The agent(s) supplied by CTEP, DCTD, NCI used in this protocol is/are provided to the NCI under a Collaborative Agreement (CRADA, CTA, CSA) between the Pharmaceutical Company(ies) (hereinafter referred to as "Collaborator(s)") and the NCI Division of Cancer Treatment and Diagnosis. Therefore, the following obligations/guidelines, in addition to the provisions in the "Intellectual Property Option to Collaborator" (http://ctep.cancer.gov/industryCollaborations2/intellectual_property.htm) contained within the terms of award, apply to the use of the Agent(s) in this study:

1. Agent(s) may not be used for any purpose outside the scope of this protocol, nor can Agent(s) be transferred or licensed to any party not participating in the clinical study. Collaborator(s) data for Agent(s) are confidential and proprietary to Collaborator(s) and shall be maintained as such by the investigators. The protocol documents for studies utilizing Agents contain confidential information and should not be shared or distributed without the permission of the NCI. If a copy of this protocol is requested by a patient or patient's family member participating on the study, the individual should sign a confidentiality agreement. A suitable model agreement can be downloaded from: <http://ctep.cancer.gov>.
2. For a clinical protocol where there is an investigational Agent used in combination with (an)other Agent(s), each the subject of different Collaborative Agreements, the access to and use of data by each Collaborator shall be as follows (data pertaining to such combination use shall hereinafter be referred to as "Multi-Party Data"):

- a. NCI will provide all Collaborators with prior written notice regarding the existence and nature of any agreements governing their collaboration with NCI, the design of the proposed combination protocol, and the existence of any obligations that would tend to restrict NCI's participation in the proposed combination protocol.
- b. Each Collaborator shall agree to permit use of the Multi-Party Data from the clinical trial by any other Collaborator solely to the extent necessary to allow said other Collaborator to develop, obtain regulatory approval or commercialize its own Agent.
- c. Any Collaborator having the right to use the Multi-Party Data from these trials must agree in writing prior to the commencement of the trials that it will use the Multi-Party Data solely for development, regulatory approval, and commercialization of its own Agent.

3. Clinical Trial Data and Results and Raw Data developed under a Collaborative Agreement will be made available to Collaborator(s), the NCI, and the FDA, as appropriate and unless additional disclosure is required by law or court order as described in the IP Option to Collaborator (http://ctep.cancer.gov/industryCollaborations2/intellectual_property.htm). Additionally, all Clinical Data and Results and Raw Data will be collected, used and disclosed consistent with all applicable federal statutes and regulations for the protection of human subjects, including, if applicable, the *Standards for Privacy of Individually Identifiable Health Information* set forth in 45 C.F.R. Part 164.
4. When a Collaborator wishes to initiate a data request, the request should first be sent to the NCI, who will then notify the appropriate investigators (Group Chair for Cooperative Group studies, or PI for other studies) of Collaborator's wish to contact them.
5. Any data provided to Collaborator(s) for Phase 3 studies must be in accordance with the guidelines and policies of the responsible Data Monitoring Committee (DMC), if there is a DMC for this clinical trial.
6. Any manuscripts reporting the results of this clinical trial must be provided to CTEP by the Group office for Cooperative Group studies or by the principal investigator for non-Cooperative Group studies for immediate delivery to Collaborator(s) for advisory review and comment prior to submission for publication. Collaborator(s) will have 30 days from the date of receipt for review. Collaborator shall have the right to request that publication be delayed for up to an additional 30 days in order to ensure that Collaborator's confidential and proprietary data, in addition to Collaborator(s)'s intellectual property rights, are protected. Copies of abstracts must be provided to CTEP for forwarding to Collaborator(s) for courtesy review as soon as possible and preferably at least three (3) days prior to submission, but in any case, prior to presentation at the meeting or publication in the proceedings. Press releases and other media presentations must also be forwarded to CTEP prior to release. Copies of any manuscript, abstract and/or press release/ media presentation should be sent to:

Email: [contact]

The Regulatory Affairs Branch will then distribute them to Collaborator(s). No publication, manuscript or other form of public disclosure shall contain any of Collaborator's confidential/proprietary information.

APPENDIX A PERFORMANCE STATUS CRITERIA

ECOG Performance Status Scale		Karnofsky Performance Scale	
Grade	Descriptions	Percent	Description
0	Normal activity. Fully active, able to carry on all pre-disease performance without restriction.	100	Normal, no complaints, no evidence of disease.
		90	Able to carry on normal activity; minor signs or symptoms of disease.
1	Symptoms, but ambulatory. Restricted in physically strenuous activity, but ambulatory and able to carry out work of a light or sedentary nature (e.g., light housework, office work).	80	Normal activity with effort; some signs or symptoms of disease.
		70	Cares for self, unable to carry on normal activity or to do active work.
2	In bed <50% of the time. Ambulatory and capable of all self-care, but unable to carry out any work activities. Up and about more than 50% of waking hours.	60	Requires occasional assistance, but is able to care for most of his/her needs.
		50	Requires considerable assistance and frequent medical care.
3	In bed >50% of the time. Capable of only limited self-care, confined to bed or chair more than 50% of waking hours.	40	Disabled, requires special care and assistance.
		30	Severely disabled, hospitalization indicated. Death not imminent.
4	100% bedridden. Completely disabled. Cannot carry on any self-care. Totally confined to bed or chair.	20	Very sick, hospitalization indicated. Death not imminent.
		10	Moribund, fatal processes progressing rapidly.
5	Dead.	0	Dead.

APPENDIX C INTEGRAL BIOMARKER ASSAY

Patients will be enrolled on the trial based on any commercially available CLIA-certified assay using somatic tissue testing like Caris, FoundationOne, or Oncomine or cfDNA assays like FoundationAct or Guardant. Below are publically available specimen instructions and assay specifications:

Caris

Caris_Specimen_Pre_Caris_Technical_Specifications.pdf

FoundationOne

FoundationAct_Specimen_Instructions.pdf

Oncomine

Oncomine-comprehensive-assay-v3-flyer.pdf

FoundationAct

FoundationAct_Specimen_Instructions.pdf

Guardant

guardant360_specification-sheet.pdf

APPENDIX D INTEGRATED BIOMARKER - METABOLOMICS

As of May 14, 2018, the Biomarker Review Committee (BRC) of the Cancer Therapy Evaluation Program (CTEP) has approved of the Mayo Clinic Metabolomics Resource Core for the quantification of serum glutamine, glutamate, aspartate and asparagine.

CB-839 is a bioavailable oral glutaminase inhibitor which disrupts glutamine anaplerosis into the TCA cycle by inhibiting the conversion of glutamine to glutamate. Thus, less carbon substrate from glutamine will enter into the TCA cycle. Hence, the investigators hypothesize that if there is effective inhibition of glutaminase (GLS1) in patients with different malignancies being treated with CB-839, the levels of glutamine will increase but the concurrent levels of glutamate and aspartate will decrease compared to baseline values.

Description of Assay

This assay will be used as a pharmacodynamic marker for response to the glutaminase inhibitor drug CB-839.

L-Asparagine, L-Aspartic Acid, L-Glutamine, L-Glutamic Acid are measured by liquid chromatography mass spectrometry (LC-MS). Briefly, serum samples are spiked with internal standards then deproteinized with cold methanol followed by centrifugation at 10,000 g for 5 minutes. The supernatant is immediately derivatized with 6-aminoquinolyl-N-hydroxysuccinimidyl carbamate according to Waters' AccQ-Fluor Kit. A 10-point calibration standard curve underwent similar derivatization procedure after the addition of internal standards. Both derivatized standards and samples are analyzed on a triple quadrupole mass spectrometer coupled with an Ultra Pressure Liquid Chromatography system. Data acquisition is done using select ion monitor (SRM). Concentrations of each unknown are calculated against each perspective calibration curve.

APPENDIX E ASSAY INFORMATION

Next-generation sequencing assays (WES and RNA-Seq) will be performed at the Molecular Characterization Laboratory on the purified DNA and RNA aliquots provided by the Biorepository. Reverse Phase Protein Array (RPPA) will be performed at the University of Texas MD Anderson Cancer Center (MD Anderson) on snap-frozen tissue provided by the Biorepository.

Whole-Exome Sequencing/Targeted-Exome Sequencing (WES/TES)

DNA libraries will be generated using the Agilent SureSelect XT Target Enrichment System, and quantitated fluorescence based quantitation. Library samples are then loaded on a flow cell prior to sequencing on a NovaSeq 6000 or NovaSeq X.

RNA-Seq

RNA libraries will be generated using the Illumina RNA Exome kit and final libraries are quantified by a fluorescence quantitation. Library samples are loaded onto a flow cell and sequenced on a NovaSeq 6000 or NovaSeq X.

Reverse Phase Protein Array (RPPA)

Frozen tumors will be lysed and protein extracted. Lysates will be manually serial-diluted in 5 two-fold dilutions with lysis buffer and printed on nitrocellulose-coated slides using an Aushon Biosystems 2470 arrayer. Slides will be probed with approximately 300 validated primary antibodies followed by detection with appropriate Biotinylated secondary antibodies (Goat anti-Rabbit IgG, Goat anti-Mouse IgG, or Rabbit anti-Goat IgG). The signal obtained will be amplified using a Cytomation-catalyzed system of Avidin-Biotinylated Peroxidase (Vectastain Elite ABC kit from Vector Lab) binding to the secondary antibody and catalyzing Tyramide-Biotin conjugation to form insoluble biotinylated phenols. Signals will be visualized by a secondary streptavidin-conjugated HRP and DAB colorimetric reaction. The slides will be scanned, analyzed, and quantified using Array-Pro Analyzer software (MediaCybernetics) to generate spot intensity (Level 1 data).

Please refer to the MD Anderson RPPA Core Facility website for additional details including workflow and data processing:

<https://www.mdanderson.org/research/research-resources/core-facilities/functional-proteomics-rppa-core/rppa-process.html>

APPENDIX F CYP2C9 SUBSTRATES

CYP2C9 Substrates with a narrow therapeutic index*

- S-Warfarin (anticoagulant)
- Phenytoin (antiepileptic)

*Narrow therapeutic index is defined as “CYP substrates with narrow therapeutic range refers to drugs whose exposure-response relationship indicates that small increases in their exposure levels by the concomitant use of CYP inhibitors may lead to serious safety concerns (e.g., Torsades de Pointes).”

<http://www.fda.gov/drugs/developmentapprovalprocess/developmentresources/druginteractionslabeling/ucm093664.htm>

Other CYP2C9 Substrates

- [NSAIDs \(analgesic, antipyretic, anti-inflammatory\)](#)
 - [celecoxib](#)
 - [lornoxicam](#)
 - [diclofenac](#)
 - [ibuprofen](#)
 - [naproxen](#)
 - [ketoprofen](#)
 - [piroxicam](#)
 - [meloxicam](#)
 - [suprofen](#)
- [fluvastatin \(statin\)](#)
- [sulfonylureas \(antidiabetic\)](#)
 - [glipizide](#)
 - [glibenclamide](#)
 - [glimepiride](#)
 - [tolbutamide](#)
 - [glyburide](#)
- [irbesartan \(to treat hypertension\)](#)
- [losartan \(to treat hypertension\)](#)
- [sildenafil \(in erectile dysfunction\)](#)
- [terbinafine \(antifungal\)](#)
- [amitriptyline \(tricyclic antidepressant\)](#)
- [fluoxetine \(SSRI antidepressant\)](#)
- [nateglinide \(antidiabetic\)](#)
- [rosiglitazone \(antidiabetic\)](#)
- [tamoxifen \(SERM\)](#)
- [torasemide \(loop diuretic\)](#)
- [ketamine](#)

APPENDIX G MEDICATION DIARY

Study Name: A Phase II Basket Trial of Glutaminase Inhibitor (BeGIN) Telaglenastat (CB-839) HCl in Patients with NF1 Aberrations, NF1 Mutant Malignant Peripheral Nerve Sheath Tumors (MPNST), KEAP1/NRF2 and LKB1 Aberrant Tumors

CTEP Study ID: 10220

Patient Initials: _____

Patient Identification Number: _____

Instructions to the patient:

PLEASE complete and return this dosing diary along with any unused Telaglenastat (CB-839) HCl and the container(s). You will receive a new dosing diary for each treatment cycle. Thank you for your participation in the very important study!

You will take: Telaglenastat (CB-839) HCl

Each time you take the Telaglenastat (CB-839) HCl study medication, your dose is 800 mg and is made up of four 200 mg tablets.

How to store your Telaglenastat (CB-839) HCl study medication

The Telaglenastat (CB-839) HCl study medication must be stored at room temperature (below 30°C/86°F) at all times. Please read the medication label for additional storage instructions.

How to take your Telaglenastat (CB-839) HCl study medication

- The Telaglenastat (CB-839) HCl study medication is to be taken twice daily for 28 days (1 cycle is 28 days).
- Each dose is taken orally (by mouth) with food around the same time each morning or evening. Administer the first dose immediately after breakfast, the second dose approximately 12 hours later.
 - Please note that on Cycle 1 Days 1 and 15, your morning dose of Telaglenastat (CB-839) HCl will be taken while fasting (at least 8 hours without eating or drinking anything but water).

If you miss the daily dose according to the schedule,

- The dose should be taken as soon as possible, but not more than 3 hours after the missed dose was scheduled.
- Vomited doses should not be made up.

How to complete your Telaglenastat (CB-839) HCl dosing diary

It is very important that you complete this dosing diary as accurately as possible and bring it

completed along with all remaining study medication (used and unused containers) to your next clinic visit.

Please fill-in this dosing diary each day that you are scheduled to take study medication. Write the date in the box marked Date. Please record the exact time you took your study medication and how many tablets taken.

It is important that you do not miss any of your study medication, but if you do please provide a reason in the “Comments” box along with any other comments you would like the doctor to know.

Cycle number: _____

Start date: _____

Patient Signature: _____

Cycle number: _____

Start date:

Patient Identification Number:

DAY	Date (MM/DD/YYYY)	Morning Dose		Evening Dose		Comments: Use the space below to make notes about things you would like to tell the doctor (including reasons for missed dose, unusual symptoms you experience, other medicine you have taken and anything else you think would be of interest.)
		Time Tablets taken	Number of tablets taken	Time Tablets taken	Number of tablets taken	
1						
2						
3						
4						
5						
6						
7						
8						
9						
10						
11						
12						
13						
14						
15						

DAY	Date (MM/DD/YYYY)	Morning Dose		Evening Dose		Comments: Use the space below to make notes about things you would like to tell the doctor (including reasons for missed dose, unusual symptoms you experience, other medicine you have taken and anything else you think would be of interest.)
		Time Tablets taken	Number of tablets taken	Time Tablets taken	Number of tablets taken	
16						
17						
18						
19						
20						
21						
22						
23						
24						
25						
26						
27						
28

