Amendment 05/ Version #13/ May 30, 2023
Amendment 06/Version #14/January 3, 2025

SCHEMA

*Within each cohort, we will employ an optimal Simon two-stage design. Specifically, within each cohort, we will enroll 9 patients, and if 0 respond, the study will be stopped early for futility within that cohort. Otherwise, an additional 18 patients will be enrolled, and if there are 4 or more responses out of the total sample of 27 patients, we will conclude that the treatment is worthy of further consideration within that cohort. This design has an overall type-I error rate of 5% (one-sided) within each cohort, and provides 88% power to reject the null hypothesis that the response rate is 0.05 when the true response rate is 0.25. Within a given cohort, this design has a 63% chance of stopping early and an expected total enrollment of 15.7 patients under the null hypothesis (i.e. if the true response rate were 0.05).

The Recommended Phase 2 dose for Telaglenastat (CB-839) HCl monotherapy is 800 mg BID. We will use this as the starting dose for this Basket trial. If patient develops toxicity then the dose can be reduced as per table below:

Dose Reductions of Telaglenastat (CB-839) HCl	
Dose Level	Telaglenastat (CB-839) HCl Dose
Starting dose	800 mg BID
First dose reduction	600 mg BID
Second dose reduction	400 mg BID
Third dose reduction	Discontinue Telaglenastat (CB-839) HCl

TABLE OF CONTENTS

TITLE PAGE

SCHEMA.....	4
TABLE OF CONTENTS.....	5
1. OBJECTIVES.....	8
1.1 Primary Objectives.....	8
1.2 Secondary Objectives.....	8
1.3 Exploratory objectives:	8
2. BACKGROUND	8
2.1 Study Disease(s).....	8
2.2 Telaglenastat (CB-839) HCl	10
2.3 Rationale	13
2.4 Correlative Studies Background	18
3. PATIENT SELECTION	23
3.1 Eligibility Criteria	23
3.2 Exclusion Criteria	24
3.3 Inclusion of Women and Minorities	25
4. REGISTRATION PROCEDURES	25
4.1 Investigator and Research Associate Registration with CTEP	26
4.2 Site Registration.....	28
4.3 Patient Registration.....	29
4.4 General Guidelines.....	30
5. BIOMARKER, CORRELATIVE, AND SPECIAL STUDIES.....	31
5.1 Summary Table for Specimen Collection.....	31
5.2 Specimen Procurement Kits and Scheduling	32
5.3 Specimen Tracking System Instructions.....	33
5.4 Specimen Collection	36
5.5 Shipping Specimens from Clinical Site to the EET Biobank	39
5.6 Shipping to the Mayo Clinic Cancer Center Pharmacology Shared Resource.....	41
5.7 Biomarker Plan	42
5.8 Integrated Correlative Studies.....	44

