6. TREATMENT PLAN

6.1 Agent Administration

Treatment will be administered on an outpatient basis. Reported adverse events and potential risks are described in Section 10. Appropriate dose modifications are described in Section 7. No investigational or commercial agents or therapies other than those described below may be administered with the intent to treat the patient's malignancy.

This phase 2 basket clinical trial utilizes single agent CB 839 HCl at the recommended phase 2 dose at 800 mg (Table 2 and 3).

Table 2. Treatment Plan for Telaglenastat (CB-839) HCl as a single agent	
Category	Treatment Plan
Telaglenastat (CB-839) HCl agent dose	800 mg
Telaglenastat (CB-839) HCl administration and schedule	Telaglenastat (CB-839) HCl dose by mouth twice daily, approximately 12 hours apart, immediately after a meal on day 1 to day 28, repeated every 28 days
Duration of treatment	Repeated every 28 days until unacceptable toxicity or disease progression. Refer to Section 6.3 for additional stopping criteria.
Duration of the study	Upon completion of follow-up procedures.
Duration of follow-up	Every 3 months (\pm) 14 days after the last administered treatment dose

If patient develop toxicity then the dose can be reduced as per Table 3.

Table 3. Dose Reductions of Telaglenastat (CB-839) HCl	
Dose Level	Telaglenastat (CB-839) - HCl Dose

Starting dose	800 mg BID
First dose reduction	600 mg BID
Second dose reduction	400 mg BID
Third dose reduction	Discontinue Telaglenastat (CB-839) HCl

The patient will be requested to maintain a medication diary of each dose of medication. The medication diary will be returned to clinic staff at each clinic visit.

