7. DOSING DELAYS/DOSE MODIFICATIONS

Based on available data, adverse events that are most likely to be observed with Telaglenastat (CB-839) HCl treatment include fatigue, gastrointestinal events (nausea, vomiting, anorexia), photophobia and elevated liver function tests. Careful application of the dose modification guidelines and close observation of the subjects should minimize the potential risk of dosing

with Telaglenastat (CB-839) HCl. The study personnel must be able to recognize and diagnose these potential adverse events and initiate prompt intervention. Guidelines for Telaglenastat (CB-839) dosage modification for clinically significant non-hematological and hematological toxicities that cannot be clearly determined to be unrelated to study drug, as well as for their management, are listed below.

Dose Level	Telaglenastat (CB-839) - HCl Dose
Starting dose	800 mg BID
First dose reduction	600 mg BID
Second dose reduction	400 mg BID
Third dose reduction	Discontinue Telaglenastat (CB-839) HCl

Dose Modification Guidelines for Hematologic Toxicity

Toxicity Grade (CTCAE v5)	Telaglenastat (CB-839) HCl
Grade 3/4 Anemia (< 8.0 g/dL Hgb)	Hold and resume at the same dose level upon resolution to \leq Grade 1 or baseline
Grade 3/4 Neutropenia (ANC < 1000/ μ L)	Hold and resume at the same dose level upon resolution to \leq Grade 1 or baseline.
Grade 3/4 Thrombocytopenia (Platelets < 50,000/ μ L)	Hold and resume at the same dose level upon resolution to \leq Grade 1 or baseline.

ANC = absolute neutrophil count, Hgb = hemoglobin.

Dose Modification Guidelines for Nonhematologic Toxicity

Toxicity Grade (CTCAE v5)	Telaglenastat (CB-839) HCl
Nonhematologic laboratory Grade \geq 3 events determined to be clinically significant and attributable to study drug(s), except for abnormal liver tests	If symptoms are not tolerable, hold and resume at the same dose level upon recovery to \leq Grade 1 or baseline. If toxicity recurs, hold and restart at next lower dose.

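### The Appendix G diary tells every patient to take 800 mg (four tablets), which is wrong for anyone reduced to 600 mg or 400 mg twice daily

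*Combined protocol and SAP*

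**What the plan says.** Appendix G instructs the patient that at each dosing time "your dose is 800 mg and is made up of four 200 mg tablets". It adds "You will receive a new dosing diary for each treatment cycle", so the same template is in use after a dose reduction. The spaces to be filled in are the patient's initials and identifier, cycle number, start date, signature and the daily log. The log has a column headed "Number of tablets taken". Nothing on the form states the prescribed dose or tells the patient to follow other directions. It refers to the medication label only for storage.

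The protocol body sets three dose levels: 800, 600 and 400 mg twice daily. The Schema says "If patient develops toxicity then the dose can be reduced as per table below", and Section 6.1 repeats the rule: "If patient develop toxicity then the dose can be reduced as per Table 3". Section 7 then gives the triggers:

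- **Reduction directed.** After Grade 3 or higher ALT, AST or bilirubin elevation, treatment is held and restarted lower. For Grade 3 or higher non-liver, nonhematologic laboratory "events determined to be clinically significant and attributable to study drug(s), except for abnormal liver tests", the first step, if symptoms are not tolerable, is to hold and resume at the same dose. After that, "If toxicity recurs, hold and restart at next lower dose".
- **Reduction discretionary.** Drug-related Grade 2 liver tests lasting more than a week, and Grade 3 non-laboratory adverse events.

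On collection of the diary, Section 6.1 says "The medication diary will be returned to clinic staff at each clinic visit".

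**The concern.** The dosing rule is consistent wherever the protocol body states it. The fault is confined to one patient-facing sentence that is true only at the starting dose. Nothing in the available text tells the site to alter that sentence after a reduction, and no reduced-dose version of the diary appears.

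The patients exposed are those who have already had toxicity at a higher dose. Such a patient would restart treatment holding a written study instruction for the dose that was just reduced, and would be handed it again each cycle. At stake are dosing safety and compliance in a small group. The two-stage design, its error rates and the response endpoint do not depend on this sentence.

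**Working it through.** **Inputs**

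- Tablet strength 200 mg (Section 8.1.1 and Appendix G).
- Dose levels 800, 600 and 400 mg twice daily (Schema; Table 3; Section 7).
- Diary instruction: four tablets per dose, whatever the level (Appendix G).
- Newer formulation supplied in 240-count bottles (Section 8.1.1).
- Visit timing (Section 11): physical examination on Days 1 and 15 of Cycles 1 and 2, and on Day 1 from Cycle 3. Footnote 14 allows three cycles of drug at a time for patients with at least stable disease for 13 cycles and a steady dose for at least two cycles.

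**Step 1. Reproduce the diary's figure.** Tablets per dose = dose / 200 mg. At the starting dose, 800 / 200 = 4, so the diary is right there.

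**Step 2. Apply the same formula to the reduced levels and compare with four tablets.**

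| Level (twice daily) | Correct tablets per dose | Correct mg/day | mg/day if four tablets taken | Excess per dose | Excess tablets/day |
|---|---|---|---|---|---|
| 800 mg | 4 | 1600 | 1600 | 0% | 0 |
| 600 mg | 3 | 1200 | 1600 | 4/3 − 1 = 33% | (4 − 3) × 2 = 2 |
| 400 mg | 2 | 800 | 1600 | 4/2 − 1 = 100% | (4 − 2) × 2 = 4 |

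**Step 3. Largest excess before the diary is next seen.** Excess = excess tablets per day × days between diary returns, ignoring visit windows.

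| Interval | Excess at 600 mg | Excess at 400 mg |
|---|---|---|
| 7 days (Cycles 1–2, if the Day 8 and Day 22 blood draws are clinic visits) | 2 × 7 = 14 | 4 × 7 = 28 |
| 14 days (Cycles 1–2, if only Days 1 and 15 count) | 2 × 14 = 28 | 4 × 14 = 56 |
| 28 days (from Cycle 3) | 2 × 28 = 56 | 4 × 28 = 112 |
| 84 days (three-cycle supply under footnote 14) | 2 × 84 = 168 | 4 × 84 = 336 |

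These are maxima. The last row needs a patient already on a steady dose for at least two cycles, so a newly reduced patient does not qualify.

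**Step 4. Would the supply run out first?** Four tablets twice daily for 28 days is 4 × 2 × 28 = 224, so a 240-count bottle dispensed whole covers the cycle with 16 to spare. If the pharmacy dispensed exactly the reduced amount, 3 × 2 × 28 = 168 tablets would last 168 / 8 = 21 days, and 2 × 2 × 28 = 112 would last 112 / 8 = 14 days. The documents do not fix the quantity dispensed, so supply may or may not limit the error.

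**Step 5. How many patients?** This cannot be reliably estimated. For one trigger only, Section 2.2.5 reports Grade 3 liver tests in 2.3% of patients on the earlier twice-daily schedule. Taken as an assumption, that gives 0.023 × 108 ≈ 2.5 patients at full enrolment, or 0.023 × 36 ≈ 0.8 if all four cohorts stop at 9 patients. Other triggers could add to this.

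**The case against.** The strongest reply is that this is an incomplete form and not a conflict between two protocol rules, and that harm needs several safeguards to fail together. Every reduction is a clinician's decision, and the two directed reductions follow a hold and recovery, so restart depends on instruction from the site. Patients bring back the diary and all remaining drug at the next visit, which gives staff regular chances to correct both. The log already accepts a smaller tablet count.

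Some of the size figures are also open to challenge. The 14-day interval shortens to 7 days if the Day 8 and Day 22 draws are clinic visits, which the documents do not settle. The 84-day case is remote, because a qualifying patient would already have returned diaries showing four-tablet dosing. The whole-bottle supply is an assumption, since Section 8.1.1 allows tablets to be transferred to another bottle before dispensing. Section 2.2.5 describes 800 mg twice daily as safe and well tolerated, although that does not speak for patients who have already had toxicity. Finally, the Appendix B patient handout and wallet card was not in the text available, so other patient-facing wording could not be checked.

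Much of this stands as a limit on likelihood and size: the per-dose percentages are firm, while the cumulative counts are upper bounds under stated conditions. None of it makes the Appendix G sentence correct. The log records what was taken without saying what to take, and a study document should not contradict the instruction that staff give at restart.

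**Conclusion.** The point holds, at low severity. The diary sentence is correct at 800 mg twice daily and wrong at both reduced levels. The firm size is +33% per dose at 600 mg and +100% at 400 mg if the page is followed literally, with intake never above the starting dose. This rests only on the tablet strength and the protocol's own dose table. The cumulative tablet counts rest further on visit spacing and dispensing quantities that the documents leave partly open. The number of patients affected is probably small. The primary endpoint, the stage-one and final decision rules and all planned analyses are unaffected.

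**What to change.** In Appendix G, replace the fixed sentence with a field completed by site staff for the current dose level at the start of each cycle:

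`Your dose is ____ mg = ____ tablets (200 mg each), twice daily.`

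Add an instruction to the site to issue a corrected diary whenever the dose changes within a cycle. This is needed because chemistry is checked on Days 8, 15 and 22 of Cycles 1 and 2 (Section 11), so a reduction can fall between scheduled diary issues. Check the Appendix B handout for the same fixed dose at the same time.

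The cost is a one-line edit at the next amendment and a minor site task each cycle and at each mid-cycle dose change. It adds no visits, data items or analyses.
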